2.4 Data Processing Conventions

2.4.1 Baseline definition

In this study, baseline values are defined as those data collected before intervention (e.g. at baseline visit). When multiple data collections occur during the baseline period, the final data shall prevail in principle, unless explicitly stated.

2.4.2 Missing data

We will report proportions of missing values for all collected variables where needed.

Missing baseline characteristics data will be imputed by regression interpolation as appropriate.

If there is a large number of missing data on efficacy and safety, an evaluation on the missing data should be conducted before formal analysis, and the study team will propose and determine the solution before database lock.

For subjects who died within the study period, the worst scores will be assigned for all subsequent not-assessed clinical outcome measures in their analyses, as follows (Table 3).

Clinical outcomes	The worst scores
mRS	6
NIHSS	42

Table 3. The worst scores of clinical outcomes

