6.2 Study Procedures

6.2.1 Schedule of Study Activities

PRØIECT-MT

The study procedure is shown in the table below.

Procedure/Time Window	Baseline	1 day post treatment	7 days post treatment [#]	90 days post treatment	
	Pre-operation - the day of treatment*	±12 hours	±2 days	±14 days	
Informed consent	Х				
Demographics ¹	X				
Medical history ²	X				
Vital signs ³	Х	Х	Х		
Blood routine test ⁴	Х	Х			
Blood biochemistry ⁵	Х	Х			
Coagulation function test ⁶	Х	Х			
Imaging examination ⁷	Х	Х	Х		
mRS score ⁸	Х			Х	
GCS score ⁹	Х	Х	Х		
NIHSS score ¹⁰	Х	Х	Х		
Quality of life using EQ- 5D ¹¹				Х	
Inclusion/exclusion criteria evaluation ¹²	Х				
Randomization and thrombectomy treatment ¹³	Х				
Medical cost			Х	Х	
Safety evaluation ¹⁴	Х	Х	Х	Х	
Concomitant medication ¹⁵	Х	Х	Х	X	

Notes: #: at discharge or 7 days post treatment, whichever occurs first. *: The end date of surgery will be considered as the day of surgery.

- 1. **Demographics:** Age, sex, height and weight;
- 2. **Medical history:** Including medical history of stroke, carotid artery disease, cardiac disorders, peripheral arterial disease, hypertension, diabetes mellitus, and hypercholesterolaemia et al, stroke risk factors including history of smoking, alcohol drinking etc, and history of allergy (allergen);
- 3. Vital signs: Pulse, blood pressure, respiration rate, and body temperature;
- 4. **Blood routine:** Red blood cells (RBC) count, white blood cells (WBC) count, neutrophils count, lymphocytes count, monocytes count, platelets (PLT) count, and hemoglobin (HGB);
- 5. Blood biochemistry: Creatinine (Cr), blood urea or blood urea nitrogen (Urea/BUN), and glucose (Glu);
- 6. **Coagulation function:** Prothrombin time (PT), activated partial thromboplastin time (APTT), and international normalized ratio (INR);

- 7. **Imaging examination:** Data of brain imaging examinations (such as CT/CTA, MRI/MRA or DSA) performed at each visit will be collected;
- 8. **mRS score:** mRS score of subjects before this onset and mRS score at 90 days post treatment will be collected;
- 9. GCS score: GCS scores immediately before randomization, and at 1 day and 7 days post treatment will be collected;
- 10. **NIHSS score:** NIHSS scores immediately before randomization, and at 1 day and 7 days post treatment will be collected;
- 11. Quality of life using EQ-5D: EQ-5D quality of life score at 90 days post treatment will be collected.

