7.2 Methods for Statistical Analysis

Analyses will be performed based on the intention-to-treat (ITT) principle. Baseline data by treatment allocation will be reported with statistical procedures. Missing values for baseline

characteristics will be reported. Missing baseline characteristics will be imputed using regression imputation as appropriate. The primary outcome will be analyzed by means of an ordinal logistic regression. Pre-defined subgroups will be analyzed by testing for interaction between the specific baseline characteristic and treatment. Any reported SAE or discontinuation of assigned treatment due to an SAE will be classified using MedDRA.

Statistical analyses will be detailed in the pre-specified Statistical Analysis Plan (SAP).

The study consists of 2 interim analyses to be performed when 30% and 60% of the 90-day follow- up data have been collected. The independent data and safety monitoring board (DSMB) will adopt the Haybittle-Peto rule, and $\alpha < 0.001$ in the interim analysis will be considered as statistically significant. Because only 2 interim analyses will be performed, the conventional significance level ($\alpha = 0.0482$) will be used for final analysis. The DSMB will monitor SAEs (e.g. death, spontaneous intracerebral hemorrhage [sICH], and neurological deterioration) periodically, and the occurrence of excessive SAEs will trigger discussion regarding termination of the study.

8 Study Monitoring

Qualified Clinical Research Associates (CRAs) will be responsible for regular monitoring of this study according to the monitoring plan. The monitoring is to ensure that all parties involved in the clinical study comply with the requirements in the Good Clinical Practice (ICH-GCP/GCP) and other applicable regulations during the implementation of the study, to protect the rights of the subjects and ensure the compliance with the clinical study protocol/procedures, as well as the authenticity, completeness and accuracy of the collected data.

Monitoring procedures include one or more visits before study initiation, regular monitoring visits during the study according to the agreed frequency of monitoring, and monitoring visits related to site closure after the end of the study.

9 Data Management

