1.3 Study outcomes

Primary efficacy outcome:

• The primary outcome is functional outcome, defined as the mRS score shift at 90 days (± 14 days).

Secondary efficacy outcomes:

- Dichotomized mRS at 90 days after the procedure (0-1 vs. 2-6, 0-2 vs. 3-6, 0-3 vs. 4-6, 0-4 vs. 5-6, 0-5 vs. 6);
- Change in stroke severity (The National Institutes of Health Stroke Scale [NIHSS] score, the criteria for scoring are detailed in Appendix 1) at 24 hours post treatment;
- Change in stroke severity (NIHSS score) at 7 days post treatment or discharge (whichever occurs first);
- Final infarction volume;
- Technical success rate (defined as successfully navigating the guide catheter into the target vessel, and finishing the mechanical thrombectomy procedure without changing to another guide catheter);
- Reperfusion outcome (Extended Treatment In Cerebral Ischemia [eTICI] 2b or greater, eTICI 2c or greater, eTICI 3; eTICI criteria are detailed in Appendix 2) in final angiogram;
- Reperfusion outcome (eTICI 2b or greater, eTICI 2c or greater, eTICI 3) after the first pass;
- Time from groin puncture to successful reperfusion (eTICI 2b or greater, eTICI 2c or greater);
- Percentage of subjects with acceptable revascularization quality (eTICI 2b or greater, eTICI 2c or greater) within 45 min of access;
- Number of thrombectomy attempts (final) ;
- Occurrence of emboli to a new territory.

Safety outcomes:

- Deaths at 90 days (±14 days) post treatment ;
- Intracranial hemorrhage, symptomatic intracranial hemorrhage or asymptomatic intracranial hemorrhage at 7 days post treatment or discharge, whichever occurs first;
- Other serious adverse events (SAEs) adjudicated by the Clinical Events Committee;
- Any peri-procedural complications, including vessel dissection, arterial perforation, and femoral access complications, etc.

Cost Outcomes:

- Health-related quality of life using EuroQol-5 Dimension [EQ-5D] (Appendix 3);
- Utility-weighted mRS scores;

- Duration of hospitalization;
- Treatment cost.

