2.2.1 Intention-to-treat Population

The ITT population will include all randomized subjects according to ITT principles, regardless of their eligibility and any protocol deviations, in which subjects will be analyzed according to the group assigned by randomization. ITT is the primary efficacy analysis set for this study and will also be used for analyses of demographics, baseline characteristics, medical history and concomitant medication information.

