2.3.7 Cost outcomes analysis

For the EQ-5D dimensions, between-group comparisons will be done using a linear model adjusted for the prognostic factors considered in the randomization, as appropriate; the adjusted mean difference will be derived from a linear model as treatment effect sizes.

For other cost outcomes, they will need time to acquire and analyze, and hence will be presented in a secondary analysis and publication, which is out of the analysis scope of the SAP.

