3 CHANGES TO PLANNED ANALYSES FROM THE PROTOCOL

No changes of planned analyses in the protocol are made in this statistical analysis plan.

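### SAP Table 3 gives no EQ-5D value for patients who died, so the death rule cannot be carried out for EQ-5D and the model as written uses only survivors with a completed form

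*SAP*

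**What the plan says.** SAP 2.4.2 (Missing data) sets a rule for patients who die during the study: "the worst scores will be assigned for all subsequent not-assessed clinical outcome measures in their analyses, as follows (Table 3"). Table 3 has two rows, mRS at 6 and NIHSS at 42. There is no EQ-5D row.

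SAP 2.3.7 (Cost outcomes analysis) keeps EQ-5D within the SAP: "For the EQ-5D dimensions, between-group comparisons will be done using a linear model adjusted for the prognostic factors considered in the randomization", with an adjusted mean difference as the effect size. It names no index or value set. It does not say whether the five items are modelled one by one or combined, or whether the 0-100 score on the Appendix 3 form is used. The other cost outcomes, including the utility-weighted mRS, are deferred to a later analysis outside the SAP.

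On timing, Protocol 6.2.1, note 11, says: "EQ-5D quality of life score at 90 days post treatment will be collected". Neither schedule has an earlier EQ-5D assessment.

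The only other rule for missing outcomes, also in SAP 2.4.2, reads: "If there is a large number of missing data on efficacy and safety, an evaluation on the missing data should be conducted". It covers efficacy and safety, whereas SAP 1.3 lists EQ-5D as a cost outcome. Regression imputation is planned for baseline data only.

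**The concern.** A linear model leaves out any patient without an outcome value. A patient who dies before day 90 has no EQ-5D form, and the SAP supplies no substitute value. The fitted comparison is therefore conditional on survival, which is a post-randomisation event that the device may affect. The two groups of survivors are no longer the groups that randomisation made comparable.

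The choice of score and the treatment of deaths also stay open until someone has to write the program, which may be after data have been seen. With the utility-weighted mRS deferred, EQ-5D is the only quality-of-life comparison that this SAP will produce.

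**Working it through.** **Inputs.** Protocol 7.1 and SAP 1.4: control mRS 0 to 6 of 3, 9, 21, 18, 22, 6 and 21%, and a common odds ratio (cOR) of 1.43. Protocol synopsis: 920 patients for 87% power at two-sided 0.05, raised to 1074 (537 per arm) for 5% dropout and 5% crossover.

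**1. Reproduce the plan's figures.** Each cumulative odds is multiplied by 1.43.

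- mRS 0-2: 0.33/0.67 × 1.43 = 0.704, so 0.704/1.704 = 41.3%. The gain is 41.3 − 33.0 = 8.3 points (plan: 8%).
- Full BGC distribution: 4.2, 12.1, 25.0, 18.5, 19.6, 4.9 and 15.7%.
- Power at N = 920: SE² = 12/[N(1 − Σp̄³)], where p̄ is the mean of the two arms in each category. This gives SE = 0.116, and Φ(ln 1.43/0.116 − 1.96) = 86.8% (plan: 87%).
- Inflation: 920/(0.95 × 0.95²) = 1073.04, hence 1074 with equal arms.

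The design reproduces, so the same inputs can be used for deaths.

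**2. Deaths under the planned effect.** Odds of being alive: 0.79/0.21 × 1.43 = 5.380, so 84.3% are alive and 15.7% dead in the BGC arm, against 21.0% in control.

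- Of 537 per arm: 537 × 0.210 = 113 and 537 × 0.157 = 84. Together 197 of 1074 (18.3%) have no EQ-5D value.
- After 5% dropout (510 per arm), the model has at most 510 × 0.790 = 403 control and 510 × 0.843 = 430 BGC patients.
- With 5% crossover in each arm, deaths are 0.95 × 21.0 + 0.05 × 15.7 = 20.7% against 0.95 × 15.7 + 0.05 × 21.0 = 15.9%.

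**3. What conditioning on survival does to a known effect.** The documents give no EQ-5D utility or standard deviation, so the gauge used here is the mRS. Under proportional odds, dividing each arm by its own survivors gives the same odds ratio at every mRS cut:

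cOR in survivors = 0.21 + 1.43 × 0.79 = 1.34.

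For mRS 0-2 among survivors: 33.0/79.0 = 41.8% and 41.3/84.3 = 49.0%, a gain of 7.2 points.

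**4. The opposite case.** Assume mortality stays at 21% in both arms and cOR 1.43 holds among survivors only. Control survivors: 0.33/0.46 = 0.717. BGC survivors: 0.717 × 1.43 = 1.026, so 50.6%, a gain of 8.9 points. In all patients: 0.506 × 0.79 = 40.0%, a gain of 7.0 points.

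| Scenario | mRS 0-2 gain, all patients | mRS 0-2 gain, survivors |
|---|---|---|
| Planned effect (deaths 21.0% vs 15.7%) | 8.3 | 7.2 |
| Mortality unchanged, effect in survivors | 7.0 | 8.9 |

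The survivors-only figure is smaller in the first case and larger in the second.

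**The case against.** The best reply is that the sentence in SAP 2.4.2 covers every later clinical outcome measure, so EQ-5D already falls under the rule and Table 3 is merely incomplete. That reading is open, and a reader should not infer that the SAP chose a survivors-only analysis; nothing in either document says so. But the sentence points to Table 3 for its values and the table has none for EQ-5D. On either reading the rule cannot be carried out without an edit.

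Second, SAP 2.3.7 does name the dimensions, and the form has five of them with five levels each, so the worst level per item is a natural entry. This is fair: the plain reading is the dimensions, not an index. It still leaves open how five ordinal items yield an adjusted mean difference.

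Third, a reader might infer that EQ-5D has no analysis population. SAP 2.2.1 ("ITT is the primary efficacy analysis set for this study and will also be used for analyses of demographics, baseline characteristics") does not list cost outcomes, but Protocol 7.2 says "Analyses will be performed based on the intention-to-treat (ITT) principle" and SAP 3 says "No changes of planned analyses in the protocol are made in this statistical analysis plan". That largely answers who belongs in the comparison. It does not supply a value for a patient who died.

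Fourth, quality of life in survivors, shown beside deaths, is a legitimate quantity. Agreed, provided it is labelled as such. The utility-weighted mRS can also score death, although not within this SAP.

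**Conclusion.** The point holds as a gap in the death rule. As written, SAP 2.3.7 would use only survivors with a completed form and, under the plan's own inputs, would leave out about 197 of 1074 randomised patients, unevenly between arms (21.0% vs 15.7%). The change from cOR 1.43 to 1.34, and the reversal when mortality is unchanged, show that the distortion can run in either direction. These figures are on the mRS scale and assume the planned control distribution and effect; the EQ-5D difference itself cannot be sized from the documents.

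A reader might infer that the survivors-only analysis loses power. The documents do not support that: they give no utilities or variances, and the direction depends on whether BGC changes mortality.

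Severity is low. EQ-5D is a cost outcome, the sample size was not set for it, the primary analysis scores death as 6, and deaths are reported separately. No main conclusion of the trial rests on it.

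**What to change.** Before database lock:

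1. State in SAP 2.3.7 which EQ-5D score is modelled.
2. State the value that patients who died receive on that score. If the dimensions are kept, use the worst level of each. The last two anxiety/depression options in Appendix 3 of both documents are printed with the same wording, so confirm how the worst level of that item is coded. If an index is chosen, name the value set and use 0 for death, stated as a convention outside the worst-scores heading of Table 3, because some index values may lie below 0.
3. Compare all randomised patients by assigned group with that value, using rank-based or bootstrap inference because deaths cluster at one value. Survivors without a form remain missing; SAP 2.4.2 already provides for reporting the proportion missing.
4. Report the survivors-only comparison as a labelled supportive result next to 90-day deaths.

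The cost is one stated value and a few sentences, with no new data. The downside is that about 18% of patients (21% if mortality is unchanged) sit at one conventional value. If the device does not change mortality, the all-randomised difference will be smaller than the survivors-only one.

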		2)	Intracranial hemorrhage, symptomatic intracranial hemorrhage or asymptomatic intracranial hemorrhage at 7 days post treatment or discharge (whichever occurs first).
		3)	Other serious adverse events (SAEs) adjudicated by the Clinical Events Committee.
		4)	Any peri-procedural complications, including vessel dissection, arterial perforation, and femoral access complications, etc.
	4.	Cos	t Outcomes:
		1)	Health-related quality of life evaluated using EQ-5D.
		2)	Utility-weighted mRS score.
		3)	Duration of hospitalization.
		4)	Treatment cost.
	•	Ba	seline
	•	24	hours (±12 hours) post treatment
Study visits	•	7 d	ays (±2 days) post treatment or at discharge
	•	90	days (±14 days) post treatment
	•	Sa	mple Size
Statistical Analysis	We tria	base 1, wh	ed our estimations on the distribution of the mRS in the control group of the nich we derived from the intervention group of the MR CLEAN trial: mRS0:

3%; mRS 1: 9%; mRS 2: 21%; mRS 3: 18%; mRS 4: 22%; mRS 5: 6% and mRS 6:21%. Based on previous studies, we assumed a favorable treatment effect with a common odds ratio (cOR) of 1.43, corresponding to an 8% absolute increase in the rate of mRS scores of 0-2. In a simulation with 5000 runs we computed the proportion of positive trials, for a given sample size. A sample size of 920 was determined to detect the superiority with a power of 87% and two-sided alpha of 0.05. Considering 5% dropout rate and 5% crossover rate, a final sample size of 1074, 537 per arm, would be needed.

• Methods for Statistical Analysis

Analyses will be performed using the intention-to-treat (ITT) principle.

Statistical analysis will be detailed in a pre-specified Statistical Analysis Plan (SAP).

Two interim analyses would be performed when 30% and 60% of the 90-day followup data have been collected.

1 Study Background

Stroke has become the leading cause of death and adult disability in China ^[1]. According to Stroke Prevention and Treatment Report of China in 2019, there are 12.42 million stroke cases in people aged 40 years or above in China, 65% of whom are ischemic stroke. With population aging, stroke prevalence is continuously rising, bringing a heavy burden to the families and society ^[2].

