1.4 Estimation of Sample Size

In a meta-analysis ^[1] comparing BGC with conventional guide catheter, the use of balloon guide catheter improved the proportion of functional outcome by 10.8%. In this study, based on a more conservative estimate, we assume the usage of BGC would improve the function outcome by 8%. Based on the distribution of the mRS in the control group of the trial, which we derived from the intervention group of the MR CLEAN trial : mRS0: 3%; mRS 1: 9%; mRS 2: 21%; mRS 3: 18%; mRS 4: 22%; mRS 5: 6% and mRS 6:21%. We assumed a favorable treatment effect with a common odds ratio (cOR) of 1.43, corresponding to an 8% absolute increase in the rate of mRS scores of 0-2. In a simulation with 5000 runs we computed the proportion of positive trials, for a given sample size. A sample size of 1074 subjects is estimated to be able to demonstrate this treatment effect with 87% power and 5% type-1 error. This sample size also allows for 5% dropout rate and 5% crossover rate.

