2.3.5.2 Secondary efficacy outcomes

For binary efficacy outcomes (dichotomized mRS at day 90, reperfusion outcome in final angiogram, reperfusion outcome after the first pass, occurrence of emboli to a new territory, technical success rate and percentage of subjects with acceptable revascularization quality), between-group comparisons will be performed by using a Chi-squared test or Fisher's exact test when applicable. The binary secondary efficacy outcomes also will be analyzed by logistic regression analysis to provide an odds ratio and its 95% CI, if applicable. The adjustment factors are the same as those in the primary outcome analysis.

For continuous efficacy outcomes (infarction volume, the change in NIHSS score at 24 hours post treatment from baseline and change in NIHSS score at 7 days post treatment or discharge from baseline), between-group comparisons will be done using a linear model adjusted for the prognostic factors considered in the primary outcome analysis, as appropriate; the adjusted mean difference will be derived from a linear model as treatment effect sizes. In case of obvious deviation from normality of the model residuals (except if a logarithmic transformation or other common transformation could be applied), a non-parametric analysis with the Mann-Whitney U test will be used and standardized differences will be calculated. Rank-transformed data will be provided as treatment effect size.

For count variable (number of thrombectomy attempts), it will be analyzed by using a negative binomial model ^[3] with the count data as dependent variable and treatment group as fixed-effect factors adjusted for the prognostic factors considered in the primary outcome analysis, as appropriate. The model estimated event rates and its 95%

confidence intervals will be provided by treatment groups. The treatment comparison will be performed through the estimated ratio of risk rates.

For time-to-event variable (time from groin puncture to successful reperfusion), it will be analyzed using the Cox's proportional hazards model with a fixed treatment group factor and adjusted for the prognostic factors considered in the primary outcome analysis, as appropriate. The estimated hazard ratio and the corresponding two-sided 95% CI will be provided. The Kaplan-Meier curves by treatment groups will be presented.

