4 INTERIM ANALYSIS

The study consists of 2 interim analyses to be performed when 30% and 60% of the 90-day follow-up data have been collected.

The independent data and safety monitoring board (DSMB) will adopt the Haybittle-Peto rule, and $\alpha < 0.001$ in the interim analysis will be considered as statistically significant. Because 2 interim analyses will be performed as scheduled, the significance level of $\alpha = 0.0482$ will be used for final analysis.

The DSMB will monitor SAEs (e.g. death, spontaneous intracerebral hemorrhage, and neurological deterioration) periodically, and the occurrence of excessive SAEs will trigger discussion regarding termination of the study.

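### Scoring early deaths as NIHSS 42 inflates the variance of the linear change model, and the rank-test fallback has no usable effect size

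*SAP*

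**What the plan says.** SAP 2.4.2 states that, for subjects who died, "the worst scores will be assigned for all subsequent not-assessed clinical outcome measures". Its Table 3 sets that score at 6 for mRS and 42 for NIHSS.

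Change in NIHSS at 24 hours, and at 7 days or discharge, are two named secondary outcomes (SAP 1.3 and 2.1.2.2). Under SAP 2.3.5.2 both are analysed with a covariate-adjusted linear model, and "the adjusted mean difference will be derived from a linear model as treatment effect sizes".

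The same paragraph gives a fallback for residuals that obviously depart from normality. A logarithmic or other common transformation may be used if one can be applied. Otherwise the Mann-Whitney U test is used and standardised differences are calculated. The next sentence reads "Rank-transformed data will be provided as treatment effect size".

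For the primary mRS outcome, SAP 2.3.5.1 also falls back on a Mann-Whitney test, but there it names the Wilcoxon-Mann-Whitney generalised odds ratio as the effect size.

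**The concern.** On the change scale a death lies far from every typical survivor. With a baseline of 16 and a mean survivor change of -5 (both assumed), a death contributes 42 - 16 = +26, a gap of 31 points. Each percentage point of early death therefore shifts an arm's mean by about 0.31 NIHSS points and adds far more to the variance than a survivor does. A linear model of the mean is sensitive to exactly this.

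The fallback raises separate problems that need no assumptions:

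- Rank-transformed data are data. They do not estimate a treatment effect and carry no confidence interval.
- The standardised differences are given no scale, estimator or interval.
- The Mann-Whitney test drops every covariate of the planned model.
- No criterion defines an obvious departure, so the analysis of two named secondary outcomes is chosen after the residuals are seen.

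At stake is whether these two outcomes yield an interpretable, pre-specified estimate, and how much power the linear model loses if it is kept.

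**Working it through.** **1. The plan's own figure.** The control distribution is "mRS0: 3%; mRS 1: 9%; mRS 2: 21%; mRS 3: 18%; mRS 4: 22%; mRS 5: 6% and mRS 6:21"% and the SAP states: "We assumed a favorable treatment effect with a common odds ratio (cOR) of 1.43". For mRS 0-2, the odds 0.33/0.67 = 0.4925, times 1.43, give 0.7043, so 0.7043/1.7043 = 41.3%. That is +8.3 points and matches the stated 8%. Whitehead's formula gives V = N(1 - Σp̄³)/12 = 920 × (1 - 0.0348)/12 = 74.0. Then z = ln(1.43) × √74.0 = 3.077 and power = Φ(3.077 - 1.960) = 86.8%. The protocol synopsis says: "A sample size of 920 was determined to detect the superiority with a power of 87% and two-sided alpha of 0.05". Inflation gives 920/(0.95 × 0.95²) = 1073.04, rounded up to 1074. The primary-outcome figure is reproduced. The documents give no such figure for NIHSS.

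**2. Inputs for NIHSS, all assumed.** 510 evaluable per arm; baseline mean 16 (SD 5); survivor change mean -5 (SD 7); two-sided 0.05. The survivor benefit is set to give 80% power without deaths: (1.960 + 0.842) × 7 × √(2/510) = 1.228 points. The only death rate in the documents, 21%, is a 90-day figure. Only deaths before the 24-hour or 7-day/discharge assessment are scored 42, so 21% is a ceiling.

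**3. Linear model, equal early death rate p in both arms.** Variance per arm = (1 - p)·7² + p·5² + p(1 - p)·Δ², with Δ = 31 in control and 31 + 1.228 = 32.228 in the BGC arm. The mean difference is (1 - p) × 1.228.

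At p = 5%:

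- Control variance: 46.55 + 1.25 + 0.0475 × 961 = 93.45 (SD 9.67).
- BGC variance: 46.55 + 1.25 + 0.0475 × 1038.6 = 97.13 (SD 9.86).
- SE = √((93.45 + 97.13)/510) = 0.611.
- z = 1.167/0.611 = 1.909, and power = Φ(1.909 - 1.960) = 48%.

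| Early deaths | SD control / BGC | Difference | SE | z | Power |
|---|---|---|---|---|---|
| 0% | 7.00 / 7.00 | 1.228 | 0.438 | 2.802 | 80% |
| 1% | 7.63 / 7.68 | 1.216 | 0.480 | 2.535 | 72% |
| 3% | 8.73 / 8.86 | 1.191 | 0.551 | 2.163 | 58% |
| 5% | 9.67 / 9.86 | 1.167 | 0.611 | 1.909 | 48% |
| 10% | 11.54 / 11.84 | 1.105 | 0.732 | 1.510 | 33% |

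Varying survivor SD over 6-10, mean change over -3 to -6 and baseline mean over 14-17 gives 67-76% at 1%, 49-69% at 3%, 38-63% at 5% and 24-50% at 10%.

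**4. Same model, early-death odds lowered by 1.43 in the BGC arm.** With 5% in control, the BGC rate is 0.0526/1.43 = 0.0368 in odds, or 3.55%. The control mean is 0.95 × (-5) + 0.05 × 26 = -3.450. The BGC mean is 0.9645 × (-6.228) + 0.0355 × 26 = -5.084. The difference is 1.634, the SE 0.589, z = 2.77 and power 79%. Over the input ranges above it is 75-83% at 5% deaths and 78-86% at 10%. If the odds fall by only 1.2, power is 59-75% at 5%. If they rise by 1.2, it is 19-47%.

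**5. Simulation of the competing analyses, balanced deaths.** About 510 per arm, baseline 15 (SD 5), survivor SD about 6, survivor benefit 1.2-1.3 points. Ranges cover runs that differ in these inputs and in how final score depends on baseline.

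| Early deaths | Linear | Mann-Whitney, unadjusted | Adjusted ranks |
|---|---|---|---|
| 0% | 84-87% | 83% | 88% |
| 1% | 73-79% | 81-85% | 82-88% |
| 3% | 56-58% | 75-80% | 74-81% |
| 5% | 43-48% | 71-78% | 74-77% |
| 10% | 27-32% | 63-67% | 60-67% |

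With early-death odds lowered by 1.43 the linear model keeps 79-85%. In one set of those runs, adjusted ranks against linear gave 87% v 79% at 3% deaths, 89% v 79% at 5% and 92% v 83% at 10%.

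**6. How likely is the switch?** Change scores are often negative, so a plain logarithm cannot be applied, and no monotone transformation removes a cluster of deaths at the extreme. In simulation with 1% deaths, a Shapiro-Wilk test on the residuals gave p < 0.0001 in every trial. If normality is tested formally, the rank test is nearly certain to be reached. If it is judged by eye, the outcome is arbitrary.

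**The case against.** The strongest reply is that the SAP already contains its own remedy. If the 42s make the departure from normality plain, the operative analysis is the Mann-Whitney test, and the linear model's power is beside the point. This largely stands: the Mann-Whitney test recovers most or all of the loss. In some runs adjusted ranks gained 4-6 points over it and in others nothing, so a power cost from dropping covariates is not established.

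A reader might infer that the plan roughly halves power for NIHSS change. The documents do not support that as a general statement. It needs balanced early deaths of about 5% or more, and it needs the linear model to be kept. At 24 hours deaths may be few. The loss is small if early-death odds fall by the trial's own common odds ratio.

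A reader might also infer that an unadjusted rank test is the only fallback with no effect measure at all. The SAP puts a transformation first and also names standardised differences. Both are in the text, although the first is unlikely to work and the second is undefined.

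Scoring death as worst is pre-specified and reasonable, and nothing here argues against it.

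**Conclusion.** The point holds in two parts.

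The first rests on the text alone. The fallback's stated effect size is not an estimate, the standardised differences lack an estimator and interval, the switch has no criterion, and the SAP is inconsistent with its own mRS fallback.

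The second is conditional. Putting 42 for deaths into a mean-change model can cost substantial power, from about 86% to about 73-79%, 57%, 45% and 30% at 1%, 3%, 5% and 10% early deaths. This assumes balanced deaths, the inputs listed above and retention of the linear model. Power is about 79-85% if early-death odds fall by 1.43. No early death rate, NIHSS SD or NIHSS effect is in the documents, so these figures show sensitivity and do not predict the trial's power.

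Both outcomes are secondary. The primary mRS analysis and its sample size are unaffected.

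**What to change.** Before database lock, amend SAP 2.3.5.2 as follows.

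- Keep death as the worst rank, and analyse the 24-hour and 7-day/discharge NIHSS score itself. On the change scale, deaths need not rank worst: a death from baseline 30 scores +12, while a survivor going from 5 to 25 scores +20.
- Pre-specify one rank-based analysis, either proportional-odds regression or ANCOVA on ranks, with the planned covariates. Baseline NIHSS is better entered as continuous than split at the median.
- Report a generalised odds ratio or probability of superiority with a 95% CI. SAP 2.3.5.1 already names the generalised odds ratio for mRS, so the method can be reused.
- Delete the residual-triggered switch for NIHSS and the sentence on rank-transformed data. That sentence also governs infarct volume, so name an effect measure with a CI there too.
- Give the survivors' mean difference as description only, since survival is itself a post-randomisation outcome.

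The cost is SAP wording and analysis code, with no new data. The downside is that the lead estimate is no longer in NIHSS points, which the descriptive survivor difference partly offsets.
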